**Primary:**

CGM accuracy - mean absolute relative difference (MARD)

The frequency of POC glucometer use in Adjustment and Utilization phase

Secondary:

- CGM accuracy at detection of hypo or hyperglycemia episodes when compared with POC monitors. (MARD for readings <70g/dl, >180g/dl, >250g/dl)
- CGM accuracy for detecting time in range (70-180 g/dl MARD).
- Number of CGM alarms and the clinical result of these alarms: nurse notification, treatment of hypo or hyperglycemia episodes, treatment for rapid declining glucose alarms.
- Time in therapeutic range for glucose as measured by CGM and POC glucose monitor.
- Detection of medications, clinical parameters or diagnoses that would interfere with CGM reading.
- Effect of CGM use on length of hospital stay.

Clinical safety measures:

- Patients with severe hypoglycemia episodes (POC glucose check below 50 mg/dl).
- Patients with DKA or HHS diagnoses after admission and enrollment in the study.
- Number of sensors with failure.
- Number of sensors removed for procedure.
- Number of sensor related skin reaction (contact dermatitis, infection)

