Continuous Glucose Monitor (CGM) Use in COVID-19 Patients

NCT04756141

10/15/2020

General Study Information

Principal Investigator: [name]

Study Title: Continuous Glucose Monitor (CGM) Use in COVID-19 Patients

Protocol version number and date: Ver1, 10/15/2020

Research Question and Aims

Hypothesis: CGM (continuous glucose monitor) used in the hospital in patients with COVID-19 will be as accurate as POC (point of care) glucose monitors. Provider acknowledgement CGM alarms of rapidly changing glucose trends will prevent episodes of hyper and hypoglycemia. If CGMs are found to be accurate, then their information can be used to monitor glucose level, and POC glucometer check frequency can be safely decreased to limit staff exposure to COVID19 patients and to decrease the use of personal protective equipment.

Aims, purpose, or objectives:

1. To determine if CGMs worn in the non-ICU hospital setting by patients with a diagnosis of COVID-19 and diabetes have adequate accuracy for blood glucose monitoring when compared to point-of-care capillary glucose measurement.
2. To determine if CGM use will decrease the frequency of POC (point of care) glucometer checks done in patients with COVID-19 diagnosis.
3. To determine if alerts given by CGMs worn by patients with diabetes and COVID19 would prevent episodes of hyperglycemia and hypoglycemia.

Background:

Diabetes Mellitus (DM) affects approximately 34.2 million (10.5%) Americans. Hyperglycemia and hypoglycemia in hospitalized patients have been associated with unfavorable clinical outcomes, including higher rates of sepsis, deconditioning, mortality and longer hospital stay. Untreated hypoglycemia may lead to neurological damage, cognitive decline, seizures and coma. Additionally, the management of the diabetic complications doubles the inpatient cost per capita compared to non-diabetic patients.

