COVID-19 pandemic has led to increase hospitalization for patients with diabetes mellitus. Current guidelines recommend treatment with high dose of steroids for COVID-19 patients requiring oxygen supplementation. This therapy leads to hyperglycemia in patients with known DM, but also in patients without previous diagnosis of diabetes. Hyperglycemia treated with insulin could lead to hypoglycemic episodes, especially in frail and very sick patients. Close monitoring of blood glucose is imperative in these patients.

The blood glucose monitoring with POC blood glucose monitors is done at bedside by nursing staff. This requires direct contact with the patient and nurse presence in the room. Depending on frequency of glucose monitoring this presence ranges from 4 times per day to every hour if patients are receiving therapy with IV insulin. Patients with COVID-19 require modified airborne isolation and nursing staff has to use PPE when entering patients' rooms.

A few pilot studies had evaluated the use of CGMs in patients with COVID19 with the aim of reducing hypo and hyperglycemia episodes and nursing staff exposure.

Manufacturers (DEXCOM and ABBOTT) are providing CGM sensors and readers to be used in COVID19 patients with the aim of decreasing the use of health care resources (PPEs) and health care providers' effort during the pandemic. Even if these sensors are not approved by FDA to be used in inpatient setting, FDA has allowed manufacturers to provide these devices to be used in COVID19 patients "to allow hospital staff to remotely monitor glucose in patients to reduce patient interaction, limiting viral exposure by hospital staff and preserving PPE."

With this study we aim to determine if CGMs are as accurate as POC glucometers, if CGM alerts can reduce episodes of hypo and hyperglycemia, and if by using CGM data to dose insulin we can decrease the number of finger-sticks and nurse exposure to COVID19 patients.

Study Design and Methods

Methods:

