Two flow-sheet protocols will be made available to nursing staff with instructions on data collection and insulin management: one for IV insulin infusion and one for SQ insulin. Nursing staff will choose the appropriate protocol at the time of CGM placement based on the type of insulin the patient is receiving. If the patient is transitioned from IV insulin to SQ insulin during the course of the study, the research team will be contacted to provide instructions on safe transition from the IV insulin protocol to the SQ insulin protocol. CGM presence will be recorded by nursing in patient chart under LDA (lines, drains, airway) section. CGM state will be monitored daily by nursing team and any evidence of localized side effects (skin lesions, pain, sensor and adhesive breakdown) will be recorded in patient's chart. Nurses will be asked to report these changes to research team. Research team will survey these recordings daily and evaluate the patients and confirm these side effects. Should these local skin reactions meet criteria for discontinuation then the sensor will be removed and patient participation in research will be terminated.

After placement, CGMs will enter the “warm up phase” for 2 hours. During this period no CGM data will be displayed and nursing staff will continue BG monitoring using Point of Care (POC) glucometer per orders. Once warm up is completed, CGMs will transmit data every 5 min to the receiver phone and their data can be recorded. Nursing staff will be asked to record CGM values in patient chart.

The use of CGMs will be divided in 2 phases – “Adjustment Phase” and “Utilization Phase”. The instructions for these phases will differ for patients on IV insulin infusion vs. SQ insulin infusion and are described in detail below.

For patients receiving subcutaneous (SQ) Insulin:

Adjustment Phase

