During the first 24 hours, sensor accuracy will be assessed. Patients will continue to have their blood glucose checked with POC glucometer concomitant with CGM use. CGM readings will be recorded in chart at the same time as POC glucometer reading is obtained. The glucometer readings and CGM data at the time of glucometer readings will be compared by nursing staff. The CGM readings should not be either 15% higher or 15% lower than the corresponding POC glucometer reading. Should this CGM reading fall outside this range, a second reading will be done within 30 minutes and readings will be compared to reassess accuracy. After the patient has had sensor in place for 24 hours and at least 4 POC glucometer glucose checks have been recorded and compared against CGM values and found to fall within the above range, the research team will be notified to determine if the frequency of POC checks can be safely decreased based on CGM accuracy.

If 2 or more consecutive CGM readings do not correlate with POC glucometer values, the research team will be notified. The research team will evaluate the data and decide if the sensor should be replaced and another 24-hour cycle of adjustment phase re-initiated, or if patient participation should be terminated. Only POC glucometer readings will be used to make decision about insulin dosing and administration during this phase. When charting insulin

administration, nursing staff will manually enter the CGM readings obtained at the time of insulin administration into the chart under the “comments” on the MAR screen.

If 4 comparison points – CGM readings and POC glucometer reading – are deemed accurate (within +/- 15% of each other for all 4 readings), then patient will enter the “Utilization Phase”.

Utilization Phase

During this phase, once the research team has confirmed CGM accuracy, POC glucometer AND CGM readings will be used to make decisions about insulin dosing and administration. The use of POC glucometer will be decreased as follows:

1. POC glucometer checks will be reduced from 4 times per day (qAC and QHS) to twice per day before breakfast and at bedtime (qAM and qHS)
2. Subcutaneous insulin dose for breakfast and bedtime will be determined based on POC readings
3. Subcutaneous insulin dose for lunch and dinner will be determined based on CGM readings
4. Nursing staff will continue to record CGM readings at the time of every insulin administration in the chart under the “comments” section on the MAR

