In the “Adjustment Phase”, during the first 12 hours, sensor accuracy will be assessed. Patients will continue to have their blood glucose (BG) checked with POC glucometer concomitant with CGM use. Nursing staff will check POC BG every 1 hour for the first 12 hours (as per established IV insulin infusion protocol). CGM readings will be recorded in chart at the same time as POC glucometer reading is obtained. These readings will be entered by nursing staff under the “comments” section of the MAR screen. The glucometer readings and CGM data at the time of glucometer readings will be compared by nursing staff. The CGM readings should not be either 15% higher or 15% lower than the corresponding POC glucometer reading. Should this CGM reading fall outside this range, a second reading will be done within 30 minutes and readings will be compared to reassess accuracy. After the patient has had sensor in place for 12 hours and at least 12 POC glucometer glucose checks have been recorded and compared against CGM values, the research team will be notified to determine if the frequency of POC checks can be safely decreased based on CGM accuracy.

If 12 comparison points – CGM readings and POC glucometer reading – are deemed accurate (within +/- 15% of each other for all 12 readings), then patient will enter the “Utilization Phase”.

If 2 or more consecutive CGM readings do not correlate with POC glucometer values, the research team will be notified. The research team will evaluate the data and decide if the sensor should be replaced and another 12-hour cycle of adjustment phase re-initiated or if patient participation should be terminated.

Utilization Phase

Once CGM accuracy has been established in the “Adjustment Phase” above, the frequency of POC glucose checks will be reduced as follows:

1. POC glucometer checks will be reduced to every 2 hours
2. CGM readings will continue to be recorded hourly by nursing staff.
 - a. If CGM glucose remains in range (140-180 mg/dl), the same insulin infusion rate will be continued.
 - b. If CGM glucose is out of range (<140 or >180) then nursing staff will resume POC glucose check every 1 hour. Insulin infusion will be adjusted as needed per IV insulin infusion protocol using the POC glucometer reading **only**.
3. If IV insulin infusion dose is adjusted, nursing staff will resume POC glucometer checks every 1 hour until the POC glucose remains in range for 2 consecutive readings

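### The by-phase POC frequency endpoint cannot answer Aim 2 alone: the protocol orders a 50% cut, and only patients who meet the accuracy criterion receive it

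*Combined protocol and SAP*

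**What the plan says.** Aim 2, under Research Question and Aims, is "To determine if CGM use will decrease the frequency of POC (point of care) glucometer checks done in patients with COVID-19 diagnosis". The matching primary endpoint, under Endpoints, is "The frequency of POC glucometer use in Adjustment and Utilization phase". Outcomes measured says that the number of checks in each phase is recorded. No denominator, time unit, analysis set or split by insulin route is given. The Data Analysis Plan names Poisson or negative binomial models for counts, but POC checks are not among its examples.

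The protocol sets the schedule in each phase. For SQ insulin, Utilization Phase item 1 says "POC glucometer checks will be reduced from 4 times per day (qAC and QHS) to twice per day". For IV insulin, checks are hourly for the 12 hours of Adjustment, and then "POC glucometer checks will be reduced to every 2 hours". Entry to Utilization requires all 4 pairs (SQ) or all 12 pairs (IV) to agree to within 15%. After two or more consecutive discordant readings, the research team decides between a new sensor with another Adjustment cycle and ending participation.

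The hypothesis is partly conditional: "If CGMs are found to be accurate, then their information can be used to monitor glucose level". Its stated purpose is "to limit staff exposure to COVID19 patients and to decrease the use of personal protective equipment", and the Background hopes that "we can decrease the number of finger-sticks and nurse exposure to COVID19 patients". The Power Statement says that the pilot is to inform whether wider implementation and study are warranted. Methods provides for a change of route: "If the patient is transitioned from IV insulin to SQ insulin during the course of the study", the research team advises on the move between protocols.

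**The concern.** The endpoint reads as a before-and-after measure of what CGM use does to POC testing. Two features of the design stand between it and that meaning.

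First, the scheduled part of the contrast is an instruction. Moving a patient to Utilization halves the scheduled checks by order. Second, Utilization time comes only from patients who meet the accuracy criterion. A patient who never meets it contributes Adjustment checks and nothing to the other side.

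Staff exposure and PPE use depend on every nurse entry for every patient fitted, including the Adjustment period and patients who never pass. If few pass, the contrast can still show about half the checks removed while the saving across all fitted patients is much smaller. A decision on wider implementation could then rest on the larger figure.

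There is also a route problem. The usual schedule is 24 checks per day on IV and 4 per day on SQ. A patient who starts on IV and moves to SQ has more high-rate time early, so phase and route are confounded if routes are pooled.

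**Working it through.** The documents print no percentage reduction, so there is no stated figure to reproduce. The schedules, the entry criteria and N = 20 come from the documents. Pair agreement p, wear time and independence of pairs are assumptions.

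**1. Scheduled cut between phases.** SQ: 1 − 2/4 = 50%. IV: 1 − 12/24 = 50%.

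**2. Scheduled saving over the whole wear if everyone passes first time.** Adjustment saves nothing.
- SQ over 6 days: 1 − (4 + 5×2)/(6×4) = 1 − 14/24 = 41.7%.
- IV over 24 h: 1 − (12 + 6)/24 = 25%. Over 48 h: 1 − (12 + 18)/48 = 37.5%.

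**3. What extra checks can do to the by-phase cut.** SQ, with 0.5, 1 or 2 extra Utilization checks per day: 1 − 2.5/4 = 37.5%, 1 − 3/4 = 25%, 1 − 4/4 = 0%. IV, with all Utilization hours back on hourly checks: 0%.

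**4. All-fitted saving, SQ, 6 days, one repeat cycle.** Let q = 1 − p. Each discordant Adjustment pair adds one POC check, so an Adjustment day has a = 4 + 4q checks. The pass probability P is p⁴ if the first readings must all agree, or (1 − q²)⁴ if an agreeing second reading counts. The text leaves both readings open, so both are shown. A patient who fails twice is counted at 4 per day afterwards. No alarm checks are included.

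Rate = [P(a + 10) + (1 − P)P(2a + 8) + (1 − P)²(2a + 16)]/6, and saving = 1 − rate/4.

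At p = 0.80 on the strict reading, P = 0.4096 and a = 4.8. The rate is (0.4096×14.8 + 0.2418×17.6 + 0.3486×25.6)/6 = 19.24/6 = 3.21 per day, a saving of 19.8%.

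| p | Strict reading | Second reading counts |
|---|---|---|
| 0.80 | 19.8% | 35.8% |
| 0.90 | 32.6% | 39.6% |
| 0.95 | 38.0% | 40.7% |

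The scheduled phase contrast is 50% in every cell. Of each gap, 50 − 41.7 = 8.3 points is the mandatory first day. The rest comes from failed or repeated cycles and retests.

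**5. Alarm checks, p = 0.80, 0.5 per day.** The result depends on where they fall.
- Utilization only: by-phase drop 1 − 2.5/4.8 = 48%; all-fitted saving 13.5% to 25.9%.
- All periods: by-phase drop 1 − 2.5/5.3 = 53%; all-fitted saving 19.8 − 12.5 = 7.3% to 35.8 − 12.5 = 23.3%.

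**6. Change of route.** Take 12 h IV Adjustment (12 checks), 12 h IV Utilization (6), 1 day SQ Adjustment (4) and 3 days SQ Utilization (6). Pooled Adjustment rate: 16/1.5 = 10.67 per day. Pooled Utilization rate: 12/3.5 = 3.43 per day. The drop is 68%, although each route's scheduled cut is 50%.

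**7. Precision of a pass proportion at N = 20.** 13/20 has an exact 95% CI of 41% to 85%; 17/20 has 62% to 97%.

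**The case against.** The strongest reply is that the endpoint is informative and the data are largely there. Alarm confirmations on SQ, and STAT checks and returns to hourly testing on IV, can take the cut from 50% to nothing (step 3), and a pilot should learn this. The measure also fits the conditional hypothesis. Checks are counted in both phases, so a whole-wear rate needs little beyond adding them and recording observation time. No document says that routes will be pooled or that the analysis is restricted to patients who pass. All of this stands, and it is why the by-phase rates should be kept.

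The sizes are also open to challenge. Pairs from one sensor are probably correlated, which raises the strict pass rate above p⁴ but weakens rescue by a second reading. At p = 0.95 with second readings counted, the gap is 9.3 points and 8.3 of them are the mandatory first day, which by-phase reporting shows openly.

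An all-fitted rate has its own difficulty. Suppose p = 0.80 on the strict reading and every patient who fails stops at 24 h. Expected checks per fitted patient are 0.4096×14 + (0.5904×4 + 0.8) = 8.90, over 0.4096×6 + 0.5904×1 = 3.05 days. The pooled rate is 2.92 per day, 27% below 4. The mean of patient-level rates is 0.4096×14/6 + 3.16 = 4.12, which is 3% above 4. One summary must therefore be named in advance, with the pass proportion beside it.

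**Conclusion.** The point holds as a cheap improvement. Aim 2 is not limited to patients who pass the accuracy criterion, and the by-phase contrast alone cannot give the saving across all fitted patients. The structural part needs no assumption: 50% is ordered, while even universal first-time passing gives 42% over 6 SQ days and 25% over 24 h on IV. The range of about 20% to 41% rests on assumed p of 0.80 to 0.95, independence, 6 SQ days, one repeat cycle and no alarm checks. Taking all fitted patients as the relevant population is this review's reading of the exposure and PPE purpose; the documents do not name a denominator.

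A reader might infer four stronger things that the documents do not support.
- **The result is foregone.** It is not, because extra checks can erase the cut.
- **The saving could be as low as 14%.** That is (0.4096×14.8 + 0.5904×24.8)/6 = 3.45 per day at p = 0.80. It needs patients who fail to wear the sensor five more days with neither a repeat cycle nor termination, a path the protocol does not describe.
- **A change of route could show an 87% drop.** That needs SQ Adjustment to be skipped (24 per day against 14/4.5 = 3.11), whereas the IV section sends such patients to the SQ protocol, which opens with Adjustment.
- **A worse sensor must look better.** The by-phase drop rises from 52% to 58% as p falls from 0.95 to 0.80 only if no discordant Utilization pair is retested (1 − 2/a). If every one is, it stays at 50%.

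**What to change.** For Aim 2, define one rate: all POC checks (scheduled, retest and alarm-triggered, including the warm-up period) divided by patient-days from sensor placement to sensor removal or end of participation, in every patient fitted. Report it separately for IV and SQ insulin, with the time of patients who switch assigned to the route in use. Give a confidence interval that treats the patient as the unit. Show the usual schedule (4 per day SQ, hourly IV) as an uncontrolled reference.

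Beside it, report the number and proportion of fitted patients who reach Utilization, with an exact confidence interval. This is needed because early termination shortens the exposure of patients who never pass and so flatters the pooled rate. Keep the by-phase rates as descriptive results. No clinical rule changes.

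The cost is endpoint and analysis wording, plus recording times of phase entry and exit and of route changes. The headline reduction will probably be smaller, and with 20 patients the pass proportion will be imprecise (step 7).

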**Outcomes measured:**

CGM accuracy when compared with POC monitors.

CGM accuracy at detection of hypo or hyperglycemia episodes when compared with POC monitors.

Number of CGM alarms and the clinical result of these alarms: nurse notification, treatment of hypo or hyperglycemia episodes, treatment for rapid declining glucose alarms.

Number of POC glucometer checks in the “Adjustment Phase” and in “Utilization Phase” will be recorded.

Hospital outcomes (length of stay, mortality, readmission and mortality at 30 days)

Patient satisfaction with DM management and inpatient care overall.

Criteria for Discontinuation of Individual Participants:

Subjects can decide to discontinue entirely from the study at any time for any reason. This is documented as withdrawal of consent. Subjects can also be discontinued from the study or discontinued from the study treatment due to Investigator decision as detailed below.

1. Withdrawal of consent.
2. At the Investigator’s discretion in certain situations such as lack of compliance or serious adverse event. (A single severe hypoglycemic event resulting in seizure or LOC or DKA).
3. 2 or more hypoglycemic events based on CGM readings that do not correlate with standard finger-stick blood glucose monitor readings and decision to remove the sensor.
4. One DKA event or one episode of hyperglycemic, hyperosmolar nonketotic syndrome (HHNS).
5. Skin infection at the site of device insertion that occurs after placement of the device.
6. Skin irritation at the site of device insertion prompting the patient to request removal of the device.
7. Transfer of the patient to the ICU with intubation, shock, placement on ECMO (Extracorporeal membrane oxygenation) or deterioration of medical condition that in the judgment of the principal investigator carries an unacceptable risk for the participant.

Materials:

CGMs (G6 sensors, G6 transmitters and Phone readers) provided and purchased from DEXCOM . iPad tablets provided by Mayo Clinic IT Department.

DEXCOM G6 app software is preinstalled on phone readers.

DEXCOM Follow app will be installed on iPads present at nursing station.

Personnel:

Diabetes educators and Endocrinology APRN will provide support for nursing staff and perform the tasks listed above.

Subject Information

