The study will use data that have been collected under another IRB protocol. Include in the Methods section and enter the IRB number from which the research material will be obtained. *When appropriate, note when subjects have provided consent for future use of their data and/or specimens as described in this protocol.*

Enter one IRB number per line, add more lines as needed

Data Specimens Data & Specimens _____

Data Specimens Data & Specimens _____

Data Specimens Data & Specimens _____

Data Analysis

Power Statement:

This a pilot study to demonstrate feasibility of CGM use in COVID patients and to determine if a subsequent more extensive implementation and studying of this device will be warranted.

Data Analysis Plan:

Data will be described as percentages or means. Pearson χ^2 and Kruskal Wallis tests will be used to compare categorical and continuous variables respectively. Odds ratios, 95% confidence intervals and p-values will be reported for each model. All tests of significance will be 2-sided and the level of statistical significance will be set at p-value < 0.05 .

Mean Absolute Relative Differences will be calculated between matched pairs of POC monitors and the closest CGM reading (within 5 minutes of POC). Additionally, level of agreement between the two devices will be examined with Bland-Altman plots, with particular attention focused on detection agreement in range (70-180 g/dl). Poisson or negative binomial regression will be utilized to assess count variables such as number of alarms, nurse notification, and hypo or hyperglycemia events adjusting for patient characteristics. Finally, longitudinal analysis will be conducted to determine differences associated with medications, clinical parameters or diagnosis. Analysis will seek to define if there are any differences between CGM and POC measurement based on these changes.

Endpoints

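### Two secondary endpoints are worded as detection but measured only by MARD within glucose ranges, which does not show what share of POC lows or highs the CGM also classed as low or high

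*Combined protocol and SAP*

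**What the plan says.** The Outcomes measured section of the combined protocol and SAP lists "CGM accuracy at detection of hypo or hyperglycemia episodes when compared with POC monitors", with no metric. The Endpoints section, under Secondary, supplies one: "CGM accuracy at detection of hypo or hyperglycemia episodes when compared with POC monitors. (MARD for readings <70g/dl, >180g/dl, >250g/dl". The next bullet is "CGM accuracy for detecting time in range (70-180 g/dl MARD". (The cut-offs are printed in g/dl there and in mg/dl elsewhere; they are read here as mg/dl.) A separate secondary endpoint is "Time in therapeutic range for glucose as measured by CGM and POC glucose monitor".

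The Data Analysis Plan computes MARD between "matched pairs of POC monitors and the closest CGM reading (within 5 minutes of POC"). It adds that "level of agreement between the two devices will be examined with Bland-Altman plots", and the same sentence asks for particular attention to detection agreement between 70 and 180, without naming a statistic. It also states that "Poisson or negative binomial regression will be utilized to assess count variables such as number of alarms", and hypo- and hyperglycemia events are among the counts listed.

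No sensitivity, specificity, predictive value or CGM-by-POC cross-classification appears anywhere. Nor is there a rule for matching CGM episodes to POC episodes, or a statement of which device's reading puts a pair into a stratum.

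**The concern.** Detection is a yes/no question at a cut-off: when POC was below 70, was the CGM also below 70? MARD is a mean absolute percentage error. It discards the sign of the error and takes no account of the cut-off, so it cannot answer that question.

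The undefined stratum adds to the problem. POC is the evident reference, because the endpoint compares the CGM with POC. If the CGM reading were used to form the strata, POC lows that the CGM missed would drop out of the below-70 stratum, and its MARD would exclude exactly the readings of interest.

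At stake is a named secondary outcome that the report would leave unanswered although the planned pairs can answer it.

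**Working it through.** The plan gives no detection figure to reproduce. The check has four steps.

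**1. What each planned output delivers**

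| Output | Gives | Share of POC lows/highs also flagged by CGM? |
|---|---|---|
| MARD by stratum | error size | No |
| Bland-Altman plots | signed bias and spread | Not committed to as counts |
| Count regressions | totals of alarms and events | No; not paired |
| Time in range by device | one total per device | No; equal totals can hide different readings |

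**2. Arithmetic from the protocol's own limit**

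The SQ Adjustment Phase says "The CGM readings should not be either 15% higher or 15% lower than the corresponding POC glucometer reading". At the edge of that limit:
- 70/1.15 = 60.9, so a POC value from 60.9 to just under 70 can read 70 or more.
- 180/0.85 = 211.8, so a POC value from just above 180 to 211.8 can read 180 or less.
- 250/0.85 = 294.1, so a POC value from just above 250 to 294.1 can read 250 or less.

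**3. Illustration (all error models are assumed; the documents give none)**

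Model: CGM = POC × (1 + b + e), with e normal, mean 0 and SD s, and POC uniform in the stated interval. Then

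MARD = s√(2/π)·exp(−b²/2s²) + b[1 − 2Φ(−b/s)].

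With b = 0.08 and s = 0.06: 0.0197 + 0.0654 = 0.0851. With b = −0.08 it is the same. An unbiased sensor with equal MARD has s = 0.0851 × √(π/2) = 0.1066. The share of lows read below 70 is the average over POC of Φ((70/POC − 1 − b)/s); highs are handled likewise.

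| MARD 8.5% throughout | b = +8% | b = −8% | unbiased |
|---|---|---|---|
| POC 55-70, CGM <70 | 65.5% | 98.9% | 82.5% |
| POC 180-250, CGM >180 | 99.3% | 75.8% | 87.4% |
| POC 250-350, CGM >250 | 99.3% | 76.5% | 87.7% |
| POC 70-180, CGM also in range | 87.7% | 93.6% | 90.7% |

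Sensitivity to the assumed noise, b = ±8%:
- s = 4% gives MARD 8.1% and, for lows, 65.9% versus 99.8%.
- s = 8% gives MARD 9.3% and 64.5% versus 97.1%.

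The answer also depends on where the POC values lie. The unbiased sensor, with relative bias 0 and SD 10.7% throughout, reads 95% of lows at 55-62.5 as below 70 but 70% of lows at 62.5-70. With MARD 6% these become 99% and 76%; with MARD 12%, 89% and 65%.

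**4. Precision available**

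Adjustment-phase pairs number at least 20 × 4 = 80 if all patients are on SQ insulin and 20 × 12 = 240 if all are on IV. At an assumed 1-5% of readings below 70, that is about 1-4 or 2-12 low pairs. If all n low pairs are detected, the exact 95% lower limit is 0.025^(1/n): 16% for n = 2, 48% for n = 5, 69% for n = 10. These limits assume independent pairs.

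**The case against.** **The plan is not silent on detection.** The Bland-Altman sentence names detection agreement for 70-180, bounded by two of the three cut-offs. This stands: a reader who inferred that the plan ignores detection would go too far. The clause still carries no statistic, and the plots give bias and spread rather than detected and missed counts.

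**The numerical contrasts are less than they seem.** The Bland-Altman plots would separate the +8% and −8% sensors. The unbiased contrast comes from moving POC values nearer the cut-off, and a reported sensitivity depends on that case mix too. Both points are fair. The calculation shows only that MARD does not determine the share detected; it does not predict what this trial will find.

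**Simple sensitivity would have its own biases.** This is correct and shapes the fix.
- CGM alarms prompt POC checks, so some pairs are selected by the CGM. The IV alarms at <70 and >180 and the SQ limit of 250 coincide with endpoint cut-offs, and the SQ <85 and IV <140 alarms prompt checks as well.
- Entry to the Utilization Phase requires all 4 (SQ) or all 12 (IV) readings within 15%. If errors are independent and retests and research-team discretion are ignored, the ±8% sensors pass with probability 0.878⁴ = 59% or 0.878¹² = 21%. The unbiased one passes with probability 0.840⁴ = 50% or 0.840¹² = 12%.
- The endpoint speaks of episodes, whereas matched pairs are single readings.

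**Relabelling would be cheaper.** Calling the bullets accuracy within glucose ranges would remove the inconsistency, but it would leave the detection outcome unanswered.

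**Conclusion.** The point holds in limited form. The only metric attached to two endpoints worded as detection is stratum MARD, and the other planned outputs do not commit to detected and missed counts. Under the assumed models, one MARD of 8.5% is compatible with 65.5% or 98.9% of POC lows at 55-70 being read below 70. Those percentages rest on the assumed bias, noise and POC distribution; the conclusion that MARD does not fix the share detected does not.

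A reader might infer that missed lows put patients at risk. The documents do not support that. The low alarms (85 for SQ, 140 for IV) sit above 70, and in the same models the CGM reads below 85 in at least 99.7% of lows at 55-70.

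The pilot has 20 patients and no decision rule tied to these endpoints, so this is a modest correction that should be made. It is a gap in specification, not in data.

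**What to change.** - Define the strata by the POC value.
- From the matched pairs, report the CGM-by-POC cross-tabulation (<70, 70-180, >180, with >250 shown separately) as raw counts with the number of patients contributing.
- Derive sensitivity, specificity and in-range agreement descriptively, with patient-clustered intervals only where counts allow.
- Label the result as agreement of paired readings, not of episodes, and state that misses between POC checks cannot be estimated.
- Report adjustment-phase and utilization-phase pairs separately.
- Where the chart allows, tabulate scheduled and CGM-prompted pairs separately at every cut-off.
- Keep stratum MARD and the Bland-Altman plots as supportive.

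The cost is SAP wording and a few small tables, with no new measurements. The scheduled/prompted split may need chart reconstruction, because hourly IV checks resume either for an out-of-range CGM value or after a change in infusion dose. Results for lows will be imprecise, and positive clustering within patients would typically lower the exact limits shown above.
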